5.4 Statistical Analysis Methods

5.4.1 Difference in Percentages

The difference in percentage, given by the difference between the proportion of subjects in the vaccine group, p_2 , with the event and placebo group, p_1 , with the event is calculated using the following formula:

$$\text{Difference in percentage} = (p_2 - p_1) * 100 = \left(\frac{E_2}{n_2} - \frac{E_1}{n_1} \right) * 100 \quad (1)$$

where E_1 and E_2 are the number of events in the placebo and vaccine groups respectively, and n_1 and n_2 are the number of subjects in the placebo and vaccine groups respectively with a valid assessment.

The 95% confidence intervals for the differences in percentages will be computed using the Miettinen and Nurminen (MN) [2] method. The following formula is used for the MN CI:

$$\text{MN CI} = \left((\hat{p}_2 - \hat{p}_1) \pm Z_{1-\frac{\alpha}{2}} \sqrt{\lambda \left(\frac{\tilde{p}_2(1-\tilde{p}_2)}{n_2} + \frac{\tilde{p}_1(1-\tilde{p}_1)}{n_1} \right)} \right) * 100 \quad (2)$$

where \tilde{p}_1 and \tilde{p}_2 are the maximum likelihood estimators for p_1 and p_2 under the null hypothesis that $p_1 - p_2 = 0$ and $\lambda = \frac{n_1+n_2}{n_1+n_2-1}$ and α is the selected level of significance. All confidence intervals for the difference in percentages outlined in this SAP will be two-sided 95% confidence intervals, i.e. with $\alpha = 0.05$.

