4.2 Rationale for the Proposed Trial

The rationale for administration of HIL-214 to infants 4 months (+7 days) of age at the time of initial trial vaccine administration is based on epidemiological data which shows that the risk of norovirus AGE increases in infants aged ~6 months old [14]; the rationale for inclusion of infants 2 months (+28 days) of age at enrolment is that infants also receive the required routine childhood vaccines in the participating countries at this age as per national guidelines.

This phase 2 trial aims to evaluate the immune response to routine pediatric vaccines (diphtheria [DT] and tetanus toxoid [TT] and acellular pertussis [aP] adsorbed, hepatitis B [HepB], inactivated polio vaccine [IPV], and *Haemophilus influenzae* type b [Hib] or DTaP-Hib-IPV-HepB, rotavirus [RV1], and pneumococcal conjugate [PCV13] vaccines) when co-administered with HIL-214 at 4 and 6 months of age, compared to that of the routine pediatric vaccines co-administered with placebo. Infants will be enrolled at the age of 2 months (+28 days) and will receive their routine childhood vaccines as part of the trial at 2, 4 and 6 months of age. HIL-214 will be administered as a 2-dose regimen, the first one when the child is 4 months of age and the second one when the child is 6 months of age, concomitantly with routine pediatric vaccines. The second trial arm will receive the routine childhood vaccines, co-administered with placebo at the age of 4 and 6 months. A placebo arm is included to allow an unbiased evaluation of the immunogenicity and safety of HIL-214 when administered with routine pediatric vaccines. A target number of at least 100 subjects will be recruited in the US to obtain co-administration data for this population. This trial is designed to support the concomitant administration of routine pediatric vaccines during the planned phase 3 HIL-214 efficacy trial.

This phase 2 trial will be conducted in accordance with the protocol, International Council for Harmonisation of Technical Requirements for Pharmaceuticals for Human Use (ICH) and Good Clinical Practice (GCP) Guidelines, and applicable regulatory requirements [2].

CONFIDENTIAL

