13.1.2 Immunogenicity Analysis

Immunogenicity data will be summarized by trial arm, for each licensed vaccine and corresponding immunogenicity assay, at all relevant time points, using:

- GMTs or GMCs and GMFR (as applicable) with 95% confidence interval (CI), geometric standard deviation (GSD), and minimum and maximum values, and
- Count and percentage of subjects with antibody titers/concentrations over pre-defined threshold, count and percentage of subjects achieving seroresponse to HIL-214, and 95% CIs for the percentages, computed using exact Clopper-Pearson method [17].

Assessment of primary objective:

The primary immunogenicity objective will be assessed using 95% CIs for differences in proportion of subjects with antibody concentrations/titers above a pre-specified threshold, computed by the Miettinen and Nurminen method [18], and 95% CIs for the geometric mean ratios, computed using the analysis of variance (ANOVA) model with natural logarithm of antibody titer/concentration as the response variable and trial arm as factor. Analyses will be done by licensed vaccine; for those vaccines used in more than one country, analyses will be repeated by country.

To address non-compliance with the vaccine administration schedule, a hypothetical strategy will be used under the assumption that lack of compliance is not related to the immune response to the routine pediatric vaccines and therefore, that infants who were not compliant with the vaccination schedule do not differ from the infants who did comply with regard to their immune response measurements. Hence, the primary immunogenicity analysis will be based on infants who were compliant with the vaccine administration schedule (i.e. received all doses of routine

CONFIDENTIAL

vaccines and trial vaccine within the allowed windows). According to the treatment policy strategy, blood sample results obtained after use of concomitant medications or other vaccines will be included in the analysis. Handling of missing data resulting from missing blood draws, non-evaluable samples (not enough volume), and blood draws outside the window will be described in the SAP.

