7.4 Subgroups

Table 5 shows the routine vaccines used in each country.

Table 5: Routine Vaccines Used in Each Country

Disease(s)	Routine Vaccine	
	Panama	USA (and Puerto Rico)
DTaP-Hib-IPV-HepB	Infanrix Hexa	Vaxelis
PCV13	Prevnar 13	Prevnar 13
RV1	Rotarix	Rotarix

Since the routine vaccines used in Panama and the USA to protect against rotavirus and the pneumococcus are the same, presenting an overall summary for the endpoints related to these vaccines is planned. Analysis of the immunogenicity endpoints for rotavirus and pneumococcal vaccines will be presented both overall and by country.

As the hexavalent vaccines used will be different in Panama and the USA there is no plan to provide an overall summary for immunogenicity endpoints related to antigens contained in these vaccines.

Therefore, analysis of all immunogenicity endpoints related to the hexavalent vaccines will be presented by country only.

The following subgroups will be presented:

- Country:
 - Panama
 - USA

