For continuous variables the ANOVA models will include all non-missing data for the parameter of interest and then the weights to account for the missing data. For binary data the proportions, which will be calculated on the complete cases data, will be reweighted, and the reweighted proportions will be used in the calculation of the confidence intervals. Therefore, in Equation (1) in [Section 5.4.1](#) will be calculated as the following:

$$\text{Difference in percentage} = (p_2 - p_1) * 100 = \left(\frac{(E_3|t_3 \times w_3) + (E_4|t_4 \times w_4)}{N_2} - \frac{(E_1|t_1 \times w_1) + (E_2|t_2 \times w_2)}{N_1} \right) * 100$$

Where E_i are the number of observed events in each category t_i and N_1 and N_2 are the number of subjects in the analysis set in the placebo and vaccine groups respectively. If all observed cases are positive in both vaccine groups, then the difference will be set to 0.

Equation (2) in [Section 5.4.1](#) will be calculated as the following:

$$\text{MN CI} = \left((\hat{p}_2 - \hat{p}_1) \pm Z_{1-\frac{\alpha}{2}} \sqrt{\lambda \left(\frac{\tilde{p}_2(1-\tilde{p}_2)}{N_2} + \frac{\tilde{p}_1(1-\tilde{p}_1)}{N_1} \right)} \right) * 100$$

Where $\lambda = \frac{N_1+N_2}{N_1+N_2-1}$.

If all observed cases are positive in both vaccine groups confidence intervals will not be calculated.

In the tables the number of events will be rounded to the nearest integer value and Clopper-Pearson CIs will be calculated using the exact weight-adjusted values using the Beta distribution. If all observed cases are positive the number of events will be set to N_1 and N_2 and these values will be used to calculate the confidence intervals.

If insufficient non-missing data are collected in participants with 1 trial vaccination the vaccine groups will be pooled to give the following vaccine options:

- Placebo vaccinations only (t_1)
- At least one HIL-214 vaccination (t_2)

The above formulae will be adjusted accordingly.

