9.1.1.3 Analysis Methods

A primary immunogenicity estimand and a supplementary estimand will be created for all of the endpoints outlined in **Table 8**. Analyses will be completed for the subgroups defined in **Section 7.4**.

For the primary immunogenicity estimands a complete case analysis will be performed, meaning any subjects with missing data for the parameter of interest will be excluded from the analysis.

For the supplementary immunogenicity estimands for the primary endpoints the missing data will be accounted for by reweighting the estimates using the method of inverse probability weighting. See **Section 7.5.1** for more details.

For the binary primary immunogenicity endpoints a standard summary for the categorical outcome will be presented as well as descriptive statistics for the continuous values. Further, the difference in percentage of subjects in the vaccine group with the event and the percentage of subjects in the

placebo group with the event will be evaluated. This will be presented along with a 95% CI calculated using the Miettinen and Nurminen [2] method as shown in **Section 5.4.1**.

For all continuous primary immunogenicity endpoints the geometric mean titer/concentration (GMT/GMC) with 95% CIs and geometric standard deviation (GSD) will be calculated. The GMRs between the vaccine group and the placebo group along with a 95% CI will be calculated using the analysis of variance (ANOVA) model with natural logarithm of antibody titer/concentration as the response variable and trial arm as a factor. Where country is used as a covariate (see **Section 7.3**) the adjusted GMs will also be presented. Further details can be found in **Section 5.4.3**.

For all primary immunogenicity parameters a reverse cumulative distribution curve will be produced, with titer/concentration on the x-axis and the percentage of patients below the titer value on the y-axis. All graphs will contain the two vaccine groups which will be overlaid.

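### SAP 5.4.1 names the Miettinen-Nurminen interval but prints a pooled Wald formula; if programmed as printed it gives (0, 0) at 100% v 100% and limits that are too close near 100%

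*SAP*

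**What the plan says.** Protocol 13.1.2 commits the primary binary comparisons to 95% intervals "computed by the Miettinen and Nurminen method [18"]. SAP 5.4.1 keeps that name: the intervals "will be computed using the Miettinen and Nurminen (MN) [2] method. The following formula is used for the MN CI". Formula (2) is then the observed difference plus or minus Z times a single standard error. The restricted maximum likelihood estimates in that standard error are taken "under the null hypothesis that" p1 - p2 = 0.

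SAP 9.1.1.3 applies this to the complete-case primary analysis, with the interval "calculated using the Miettinen and Nurminen [2] method as shown in" Section 5.4.1. SAP 7.4 adds that "analysis of all immunogenicity endpoints related to the hexavalent vaccines will be presented by country only", so every binary primary endpoint gets one interval for Panama and one for the USA, and none overall. On country size, Protocol 4.2 says only: "A target number of at least 100 subjects will be recruited in the US".

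The weighted supplementary analysis in SAP 7.5.1 prints the same closed form with N1 and N2 in place of n1 and n2; these "are the number of subjects in the analysis set in the placebo and vaccine groups respectively". It also states: "If all observed cases are positive in both vaccine groups confidence intervals will not be calculated". The primary analysis has no such rule. The list of departures from the protocol in SAP Section 13 does not mention any move away from MN.

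**The concern.** The MN limits are the two values of the difference at which a score statistic reaches 1.96 in absolute value. The restricted estimates are recomputed under each candidate difference, which makes the interval asymmetric and keeps it sensible when both arms are close to 100%. Fixing the estimates at zero difference removes that property. The method name and the printed formula therefore describe two different intervals, and neither document shows which one would be programmed.

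The primary objective is to see whether HIL-214 reduces the response to the routine vaccines. With no test and no margin, the interval is the main result, and its useful content is how large a fall in the HIL-214 arm the data exclude. If results are near 100%, the printed formula makes that excluded fall look smaller than the data support. If every infant in both arms is above the threshold, it reports no uncertainty at all, and the planned forest plot would show an interval of zero width. The SAP's authors foresaw the all-positive outcome, since 7.5.1 has a rule for it, but that rule does not reach the primary analysis.

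**Working it through.** **Inputs.** Two-sided 95%, Z = 1.96 (SAP 5.4.1). Allocation 1:1, stratified by country, 400 in all (SAP 5.2). At least 100 in the US (Protocol 4.2). Exactly 100 US infants would give about 50 per arm in the US and 150 per arm in Panama, before exclusions; this is an assumption. Neither document states expected response rates, so the rates below are assumed. There is no stated interval to reproduce. Differences are HIL-214 minus placebo, in percentage points.

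**1. What formula (2) is.** Under p1 = p2 both restricted estimates equal the pooled proportion p = (E1 + E2)/(n1 + n2). With λ = (n1 + n2)/(n1 + n2 - 1), formula (2) becomes

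d ± 1.96 × sqrt(λ p(1 - p)(1/n1 + 1/n2)).

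**2. What MN is.** The limits solve |d - δ| / sqrt(λ[p2~(1 - p2~)/n2 + p1~(1 - p1~)/n1]) = 1.96, with p1~ and p2~ the maximum likelihood estimates under p2 - p1 = δ.

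**3. 100% v 100%.** Here p = 1, so formula (2) gives (0, 0) at any n. For the MN lower limit at δ = -D, the restricted estimates are 1 (placebo) and 1 - D (HIL-214). The equation D = 1.96 sqrt(λ D(1 - D)/n) solves to D = c/(1 + c), with c = 1.96² λ/n. For n = 50, λ = 100/99, c = 0.0776 and D = 0.0720. The upper limit is its mirror image, so MN gives ±7.2. The same steps give ±3.7 at n = 100 and ±2.5 at n = 150.

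**4. 48/50 v 50/50.** Formula (2): p = 98/100 and the standard error is sqrt(1.0101 × 0.98 × 0.02 × 0.04) = 0.0281. The limits are -4.0 ± 5.5 = (-9.5, 1.5). MN lower limit: at δ = -0.1353 the restricted estimates are 1 and 0.8647. Then (0.1353 - 0.04)/sqrt(1.0101 × 0.8647 × 0.1353/50) = 0.0953/0.0486 = 1.96. The MN upper limit, found by root-finding, is 3.3.

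| HIL-214 v placebo | SAP formula (2) | MN |
|---|---|---|
| 50/50 v 50/50 | (0, 0) | (-7.2, 7.2) |
| 48/50 v 50/50 | (-9.5, 1.5) | (-13.5, 3.3) |
| 98/100 v 100/100 | (-4.8, 0.8) | (-7.0, 1.8) |
| 150/150 v 150/150 | (0, 0) | (-2.5, 2.5) |
| 148/150 v 150/150 | (-3.2, 0.5) | (-4.7, 1.2) |
| 135/150 v 140/150 | (-9.6, 2.9) | (-10.0, 3.1) |

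**5. Exact coverage,** by enumerating both binomials.

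| True placebo / HIL-214 (%) | n per arm | SAP | MN |
|---|---|---|---|
| 99 / 97 | 50 | 78.0% | 98.7% |
| 99 / 97 | 75 | 89.3% | 98.3% |
| 99 / 97 | 100 | 93.6% | 95.4% |
| 99 / 97 | 150 | 92.3% | 93.8% |
| 98 / 96 | 50 | 86.4% | 97.1% |
| 98 / 96 | 150 | 94.5% | 94.3% |
| 100 / 98 | 50 | 63.5% | 99.7% |
| 100 / 98 | 150 | 80.0% | 96.8% |
| 98 / 98 | 50 | 98.7% | 98.7% |
| 95 / 90 | 50 | 94.8% | 94.7% |
| 98 / 95 | 150 | 94.7% | 94.6% |

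**6. Whether 0 is inside.** At δ = 0 the MN statistic uses the pooled proportion, so the two methods agree there by construction. All 2,601 possible results at n = 50 (51 × 51) confirm it. The discrepancy concerns only which non-zero differences are excluded.

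**7. SAP 7.5.1.** N1 and N2 count infants whose samples are missing, so using them in the variance overstates the information. As an illustration, take 40 of 50 samples observed per arm, all positive. MN is then ±8.9 on the observed 40 and ±7.2 if 50 is used. The SAP currently gives no interval for that result, so the figures show only the direction of the effect.

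**The case against.** The method is named in three places and its source paper is cited in both documents. A programmer using a standard MN routine would produce correct primary intervals, and the defect would be only a wrong formula on paper. That is possible. But SAP 5.4.1 says the printed formula is the one used, 9.1.1.3 points back to it, and the SAP names SAS without a procedure or option. If a standard routine is run, the output will not match the SAP; if the formula is followed, the protocol's method is not delivered. Either way the text needs correcting.

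The harm also depends on assumptions. The 78.0% needs 50 per arm and rates of 99% and 97%; the 63.5% needs a true placebo rate of exactly 100%. Fifty per arm follows from a recruitment floor, although exclusions could go below it. With 150 per arm at 99/97 the gap is 1.5 points of coverage, and MN itself is under 95%. With equal true rates there is no gap. All of this stands and limits the size of the point.

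The documents set no margin and no tolerable fall. The only reference value for these differences is the forest-plot line at 0, on which the two intervals never disagree. That is correct: no formal decision changes. Per-arm Clopper-Pearson limits are also planned (lower limit 92.9% for 50/50, 97.6% for 150/150), but they do not give an interval for the difference.

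Finally, N1 and N2 are natural denominators for the weighted point estimate in 7.5.1, because the weights scale the events up to the analysis set. The criticism there applies to the variance only, and it is secondary.

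**Conclusion.** The concern holds. SAP 5.4.1 names one interval and prints another, and the printed one governs the by-country primary binary endpoints. If programmed as printed, it collapses to (0, 0) when both arms are at 100%. Near 100% it puts the lower limit too close to zero: by about 4 points at 48/50 v 50/50 and about 1.6 points at 148/150 v 150/150. Coverage can fall well below 95% when a small true reduction exists in a small country. The effect is slight once rates move away from 100%, and absent for the question of whether 0 is inside.

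This rests on assumed response rates and assumed country sizes of 50 to 150 per arm. It affects the reported precision of the primary comparison and no pass/fail decision. It should be fixed before the analysis is programmed. The 7.5.1 point is a smaller, separate one.

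**What to change.** In SAP 5.4.1, replace formula (2) with the definition in step 2 of the working: the limits are the values of δ at which the score statistic equals 1.96 in absolute value, with the restricted estimates computed under p2 - p1 = δ. Name a validated MN routine and option, and state that its interval is reported at 100% v 100% in the complete-case primary analysis. Check the routine near 100% before relying on it.

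In SAP 7.5.1, stop using the zero-difference formula for the weighted analysis. If an interval is given there when all observed cases are positive, base it on the number of infants observed and not on N1 and N2. This does not imply that MN applied to weighted counts is valid; that needs its own justification.

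The cost is SAP wording and a standard routine. The price in the results is wider intervals near 100%.

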5.4.2 Geometric Mean

The geometric mean (GM) of a set of numbers x_1, x_2, \dots, x_N is calculated by taking the exponential of the mean of the logged values, as per the following formula

$$GM_x = \exp \left\{ \frac{\sum_{i=1}^N \ln(x_i)}{N} \right\}.$$

The geometric standard deviation (GSD) for the same set of numbers is given by

$$GSD_x = \exp \left\{ \sqrt{\frac{\sum_{i=1}^n \left(\ln \left(\frac{x_i}{GM_x} \right) \right)^2}{n}} \right\}.$$

The 95% confidence interval (CI) is calculated as per the following formula:

$$95\% CI = \exp \left\{ \ln(GM) \pm Z_{1-\frac{\alpha}{2}} \frac{\ln(GSD)}{\sqrt{n}} \right\}$$

where α is the selected level of confidence. All confidence intervals outlined in this SAP will be two sided 95% confidence intervals, i.e. with $\alpha = 0.05$.

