5.4.3 Geometric Mean Ratio

The geometric mean ratio (GMR) is the ratio of two different geometric means (Section Error! Reference source not found.). The GMR and corresponding 95% CI will be calculated using an analysis of variance model (ANOVA). The difference between the natural logarithm of the values and 95% CI will be calculated, with the exponential of these values being the GMR and corresponding 95% CI.

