5.4.4 Geometric Mean Fold Rise

The geometric mean fold rise (GMFR) is given by taking the mean of the natural logarithm of the fold increases (**Section 5.3.2.1**). Therefore for the fold increases fi_1, \dots, fi_n , the GMFR is

$$GMFR = \exp \sum_{j=1}^n (\log\{fi_j\} / n).$$

Which is equivalent to

$$GMFR = \frac{GM_4}{GM_2}$$

where GM_2 is the geometric mean at Visit 2 and GM_4 is the geometric mean at Visit 4.

The 95% confidence interval for GMFR will be calculated using the same method as the 95% CI for GM (outlined in **Section 5.4.2**) but using the log of the fold rises rather than the log of concentrations.

6 Sample Size

This trial is designed to be descriptive, and therefore the sample size was not determined based on formal statistical power calculations. The planned number of subjects is approximately 400, with 200 receiving HIL-214 and routine childhood vaccines and 200 receiving Placebo and routine childhood vaccines.

7 General Considerations

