9.2.1.3 Analysis Methods

For the secondary immunogenicity endpoints data will only be analysed for the patients receiving HIL-214.

A secondary immunogenicity estimand and a supplementary estimand will be created for all of the endpoints outlined in **Section 9.2.1.2**. Analyses will be completed for the two country subgroups only, defined in **Section 7.4**.

For the secondary immunogenicity estimands a complete case analysis will be performed, meaning any subjects with missing data for the parameter of interest will be excluded from the analysis.

For the supplementary immunogenicity estimands for the secondary endpoints the missing data will be accounted for by reweighting the estimates using the method of inverse probability weighting. See **Section 7.5.1** for more details.

For all binary secondary immunogenicity endpoints a standard categorical summary will be presented. SRR is defined in **Section 5.3.2.2**.

For all continuous secondary immunogenicity endpoints a standard continuous summary of the outcome will be presented alongside the GM and GMFR and their confidence intervals. Where country is used as a covariate (see **Section 7.3**) the adjusted GMs will also be presented.

For all secondary immunogenicity parameters a reverse cumulative distribution curve will be produced, with titer/concentration on the x-axis and the percentage of patients below the titer/concentration value on the y-axis. All graphs will present the two vaccine groups which will be overlaid.

Line graphs and boxplots summarizing the GMT for each trial vaccine group for the serotypes GI.1 and GII.4 will also be produced. These outputs will both have the visits of baseline and Visit 4 on the x-axis and the GMT on the y-axis, presenting data on the log scale.

Bar plots for seroresponse, with 95% CIs, will also be created with the results for placebo and HIL-214 stacked next to each other and separate sets of bars for the serotypes GI.1 and GII.4.

10 Safety Analyses

All safety analysis is defined in this section. Along with the following summaries, all safety endpoints will be listed by vaccine group. Where summaries are presented overall, after first dose and after second dose subjects will be summarised under the trial vaccine they receive for that period. If a subject receives HIL-214 for either dose they will be summarised under HIL-214 in the overall summary.

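### The 95% CIs for geometric means and fold rises (SAP 5.4.2, 5.4.4) are slightly too narrow: they use a normal quantile and an SD with divisor n

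*SAP*

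**What the plan says.** SAP 5.4.2 defines the geometric mean as the exponential of the mean log value. It defines the geometric standard deviation (GSD) as the exponential of the root mean squared log deviation from that mean, with divisor n. The interval follows: "The 95% confidence interval (CI) is calculated as per the following formula", namely exp{ln(GM) ± Z(1−α/2)·ln(GSD)/√n}. The level is explicit: "All confidence intervals outlined in this SAP will be two sided 95% confidence intervals", with α = 0.05.

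SAP 5.4.4 extends this to fold rises: "The 95% confidence interval for GMFR will be calculated using the same method as the 95% CI for GM", using log fold rises in place of log concentrations.

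Three other interval methods appear in the SAP:
- Geometric mean ratios (5.4.3): "The GMR and corresponding 95% CI will be calculated using an analysis of variance model (ANOVA".
- Differences in percentages (5.4.1): Miettinen and Nurminen.
- Single percentages, including seroresponse rates (section 9): exact Clopper-Pearson.

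On the secondary objective, SAP 9.2.1.3 says "For the secondary immunogenicity endpoints data will only be analysed for the patients receiving HIL-214", and restricts the analyses to the two country subgroups.

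**The concern.** The SD is not known; it is estimated from the sample that supplies the mean. Under normality of the log values, the pivot is then a t variable with n−1 degrees of freedom, and the SD in it has divisor n−1. The SAP formula replaces the t quantile with a smaller normal quantile, and the SD with a smaller one. Both changes act in the same direction, so the interval falls short of its stated 95% level and the reported GSD is a little low.

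The formula is used in two places:
- **Per-arm GMC/GMT summaries of the routine-vaccine antigens.** For the hexavalent antigens these are given by country only (SAP 7.4), so the smaller US group is reported on its own.
- **Secondary GMT and GMFR endpoints.** These are analysed in one arm, so they have no between-arm ratio and no ANOVA interval. In the complete-case analysis the 5.4.2 and 5.4.4 intervals are the only ones planned for them. SAP 9.2.1.3 mentions country-adjusted means, but 7.3 reserves the country covariate for overall analyses, and the secondary analyses are by country only.

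The trial is descriptive, so the intervals are a main part of what it reports and should have the coverage that their label states.

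**Working it through.** **Inputs**
- Interval and GSD formulas, α = 0.05 two-sided: SAP 5.4.2, so Z = 1.960.
- About 400 subjects, 1:1: Protocol 6.1. Hence 200 per arm.
- At least 100 US subjects: Protocol 4.2. Stratification by country: Protocol 8.6. Two countries: SAP 7.4. At the minimum target, the US has about 100/2 = 50 per arm and Panama about (400 − 100)/2 = 150 per arm. All are before exclusions.

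The documents give no power figure, SD or dropout rate, so the only figure to check is the nominal 95%.

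**Coverage.** Let s be the log-scale SD with divisor n−1. The SAP SD is s·√((n−1)/n), so the SAP half-width is c·s/√n, where c = 1.960·√((n−1)/n). With normal log values:
- Coverage = 2·F(c) − 1, where F is the t distribution function with n−1 degrees of freedom.
- Width relative to the t interval = c / t(0.975, n−1).

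The SD cancels from both expressions.

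| n | √((n−1)/n) | c | t(0.975, n−1) | Width ratio | Too narrow by | Coverage |
|---|---|---|---|---|---|---|
| 200 | 0.9975 | 1.955 | 1.972 | 0.9914 | 0.9% | 94.80% |
| 150 | 0.9967 | 1.953 | 1.976 | 0.9886 | 1.1% | 94.74% |
| 50 | 0.9899 | 1.940 | 2.010 | 0.9655 | 3.4% | 94.19% |

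Simulation with 100,000 samples per n gave 94.7%, 94.8% and 94.1%, in agreement.

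**Which part matters more.** At n=50 the normal quantile alone gives 94.43% and the n divisor alone gives 94.77%.

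**Smaller groups.** These sizes are assumptions, because no exclusion rate is stated. Coverage would be 93.98% at n=40 (4.3% too narrow), 93.62% at n=30 (5.8%) and 92.87% at n=20 (8.7%).

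**Effect on reported limits.** The log SDs below are assumed, at n=50, and limits are relative to the GM.

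| Assumed log SD | SAP limits | t limits |
|---|---|---|
| 0.8 | 0.803–1.246 | 0.797–1.255 |
| 1.2 | 0.719–1.390 | 0.711–1.406 |
| 1.6 | 0.645–1.551 | 0.635–1.576 |

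**Effect on the GSD.** ln(GSD) is low by the factor √((n−1)/n), which is 1.0% at n=50 and 0.25% at n=200.

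**The case against.** The strongest reply is that this changes almost nothing. The divisor-n SD is the maximum-likelihood estimator, and the normal interval is a standard large-sample approximation. The formula is pre-specified and reproducible. The shortfall is 0.2 points at n=200 and 0.8 points at n=50. The trial has no margin, success criterion or power calculation that uses these intervals. All of that stands, and it fixes the weight of the point.

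The comparisons that answer the primary objective are also untouched: ratios come from ANOVA and differences in percentages from Miettinen and Nurminen. That stands too.

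A reader might infer that these intervals are the only ones for the secondary objective. The documents do not support that. SAP 4.2.2 lists three secondary summaries: GMT, GMFR and seroresponse rate. Seroresponse rates carry exact Clopper-Pearson intervals, which 9.2.1.3 also plots. The statement holds for two of the three.

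A reader might also infer that every such interval is proven to cover less than 95%. That goes too far. SAP 5.3.2.3 substitutes fixed values for results below the detection or quantification limits and above the upper limit, so the log values are only approximately normal and a t interval would not be exact either. In the supplementary analyses, SAP 7.5.1 brings in inverse probability weights without spelling out the one-sample interval. The coverage figures therefore do not extend there.

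Finally, 50 is a floor for US enrolment per arm, not a forecast, and any smaller figure is an assumption. What remains is that the printed formula misses its stated level for no stated reason, although the SAP uses an exact method for single proportions.

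**Conclusion.** The point holds as a minor one. With log-normal complete-case data, the geometric mean and GMFR intervals labelled 95% cover 94.7–94.8% at the planned Panama and overall arm sizes. They cover 94.2% at the US arm size implied by the minimum target. The shortfall stays under one point for n of 50 or more and would become noticeable only if exclusions left a country group of about 20–30.

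The country sizes assume 1:1 allocation within country, exactly 100 US subjects and no exclusions. No conclusion that the plan sets out to draw would change.

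**What to change.** In SAP 5.4.2:
- Compute s, the SD of the log values, with divisor n−1, and report GSD = exp(s).
- Give the interval as exp{mean(ln x) ± t(0.975, n−1)·s/√n}.

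In SAP 5.4.4, state that the same rule applies to the log fold rises.

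Under log-normality this gives exactly 95% coverage at any group size. The cost is two lines of SAP text. No GM or GMFR point estimate changes, and no new data are needed. Log-scale interval widths grow by 1/0.9914 = 1.009 at n=200, 1/0.9886 = 1.012 at n=150 and 1/0.9655 = 1.036 at n=50, that is, by about 1–4%.
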